## BACKGROUND AND SIGNIFICANCE

Reverse total shoulder arthroplasty (RTSA) relieves pain and improves function in patients with rotator cuff-deficient arthropathy. RTSA has consistently been reported to improve forward elevation and pain, however, its effect on internal and external rotation has been less predictable. Some studies indicate that humeral component version plays a role in improvement of humeral rotation following RTSA, however, the published data is contradictory and inconclusive. Several biomechanical studies have suggested that increasing humeral component retroversion may improve external rotation, while subsequently decreasing internal rotation. Conversely, Henninger *et al.* reported on a cadaveric study that showed no differences in rotation over a range of different humeral component versions. A retrospective study by Rhee *et al.* also suggests that increasing humeral component retroversion does not affect measured internal or external rotation. However, they found that patients with neutral version may experience better function with daily activities requiring internal rotation compared to those with 20 degrees of retroversion. Prospective data on clinical outcomes comparing different humeral component versions in RTSA is currently lacking.

The proposed study is a prospective, double-blinded, randomized trial to investigate the impact of humeral component version on shoulder range-of-motion and patient-reported functional outcomes following reverse total shoulder arthroplasty.

## OBJECTIVE

- The primary objective of this study is to determine whether external rotation and internal rotation two years postoperatively is impacted by humeral component version in reverse shoulder arthroplasty
- The secondary objective is to determine whether functional outcomes two years postoperatively are impacted by humeral component version in reverse shoulder arthroplasty

## HYPOTHESIS

- Patients that receive RTSA with the humeral component positioned in 30 degrees of retroversion will have greater external rotation and worse internal rotation postoperatively than those that have 0 degrees of version.
- Patients that receive RTSA with the humeral component positioned in 0 degrees of version will have higher functional outcomes scores, due to improved internal rotation, than those that have 30 degrees of retroversion.

## RESEARCH DESIGN AND METHODOLOGY

We will perform a prospective, randomized trial with a total of 85 patients. Patients undergoing primary RTSA by Dr. [name] at Beaumont Hospital Royal Oak will be screened for eligibility. After the patient has been consented they will be randomized to one of the following two groups:

1. RTSA with humeral component positioned in 0 degrees of version
2. RTSA with humeral component position in 30 degrees of retroversion

The patient will be blinded to the study group.

## INCLUSION CRITERIA

- Patients undergoing primary reverse total shoulder arthroplasty (with Biomet component, glenosphere size 36)
- Diagnosis of cuff tear arthropathy, massive cuff tear, or primary osteoarthritis with cuff tear
- negative external rotation lag sign, ability to externally rotate beyond neutral
- Age 18 years or older

## EXCLUSION CRITERIA

- Revision arthroplasty
- Prior open shoulder surgery
- Concomitant latissimus dorsi transfer
- Diagnosis of rheumatoid arthritis, infection, acute trauma or instability
- Patients not undergoing a standard-of-care physical therapy protocol
- Pregnant, patient-reported
- Minors (under 18 years of age)
- Cognitively impaired

## ENROLLMENT AND CONSENT

Patients scheduled to undergo reverse total shoulder arthroplasty with [name] will be screened preoperatively for eligibility. Patients will be identified in the clinic and by operative schedules. Patients that meet all criteria will be contacted by personnel on the delegation of authority as a consent provider before their procedure. If the patient is interested, the research coordinator will offer to email or mail a copy of the consent for the patient to review beforehand. During the time of consent, the patient will confirm they have read and understand the consent. Patients can discuss any questions they may have with the consent provider at this time. Patients will be allowed to drop out of the study at any time before or after their procedure.

## RANDOMIZATION

The 85 patients enrolled in the study will be randomized in a 1:1 ratio to have their procedure performed either with a humeral component positioned in 0 degrees of version or 30

degrees of retroversion. Randomization assignments will be contained in sequentially numbered, opaque, sealed envelopes, which will be prepared by a statistician in the research institute. After the patient is consented, they will be assigned to a group following the treatment listed in the envelope. Key personnel not collecting data will perform randomization and inform the surgeon of the group in order to keep data collection blinded. The patient will also remain blinded to their assignment. Logs will be maintained by the randomizing personnel.

## DATA COLLECTION

Baseline data will be collected before the patient's procedure, after consent has been signed. Patients will be followed at standard-of-care follow-up appointments in the clinic at 3 months, 6 months, one year, and two years postoperatively. To help prevent dropouts, follow-up requirements will be discussed with the patient before consent and all patients will be called as each time point approaches to schedule follow-up appointments. At each appointment the patient will complete patient-reported outcomes questionnaires and will undergo a physical exam with a clinical research coordinator blinded to the patient's study group. Standard-of-care x-ray images will also be assessed.

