### DATA ANALYSIS

The range-of-motion, strength measures, patient-reported outcomes scores, and patient demographic factors will be compared between the two treatment groups. A table of descriptive summaries by treatment group will be prepared (means and standard deviations if normally distributed, median and range if not normally distributed, counts and percentages for categorical variables). Confidence intervals for the means/medians for each of the two groups will also be computed. The change from baseline as well as the absolute postoperative outcomes measurements will be used for comparison. Before comparing continuous variables, data sets will be assessed for normality using a Shapiro-Wilk Test. For normal data, an independent student's t-test will be used to compare means. A Mann-Whitney Rank Sum Test will be used for data that is ordinal or not normally distributed. The two treatment groups will be compared on categorical variables using the Fisher's Exact test.

Missing data will not be imputed, but the number of data points available at each time point postoperatively will be clearly reported in publications. For all tests, a p-value  $< 0.05$  will be considered statistically significant. A Bonferroni correction will be used to account for repeated measures and control for a Type I error. Graduate-trained engineers will analyze data with SPSS statistical software (SPSS Version 22.0, IBM, Inc).

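### Two-year questionnaires are provided for only at the clinic visit, so a patient who misses that visit has no two-year functional score, although the questionnaires need no examination

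*Combined protocol and SAP*

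**What the plan says.** The setting for follow-up is given in Data Collection: "Patients will be followed at standard-of-care follow-up appointments in the clinic at 3 months, 6 months, one year, and two years postoperatively". The same section places the questionnaires inside those visits: "At each appointment the patient will complete patient-reported outcomes questionnaires and will undergo a physical exam with a clinical research coordinator blinded" to study group. In the Schedule of Events, the questionnaire row and the physical examination row are marked at the same time points, and the two-year window is ±4 months.

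To limit dropout, Data Collection provides for a discussion of follow-up before consent and a telephone contact: "all patients will be called as each time point approaches to schedule follow-up appointments". Both encourage attendance; neither covers the case where attendance fails. Mail and email appear only under Enrollment and Consent, for sending the consent form.

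The secondary objective is to "determine whether functional outcomes two years postoperatively are impacted by humeral component version in reverse shoulder arthroplasty". The matching hypothesis is that patients at 0 degrees "will have higher functional outcomes scores, due to improved internal rotation". All four instruments under Patient Reported Outcomes are completed by the patient.

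Data Analysis compares the groups by t-test or Mann-Whitney test, on absolute values and on change from baseline. It states "Missing data will not be imputed" and promises to report how many data points are available at each time point.

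**The concern.** Rotation and strength are measured with a goniometer and a dynamometer, so they need the patient in the room. The questionnaires do not. Under the plan as written, one missed two-year visit removes both kinds of outcome, when only the first has to be lost.

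The analysis does not make up for this. A two-group test at two years, with no imputation, uses only patients who have a two-year value. Scores at 3 months, 6 months and one year do not enter that comparison.

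Two things are at stake. The first is precision in the two-year functional comparison. The second is bias: patients who skip a late visit may be doing well and see no need to come, or doing poorly, and under this plan their two-year function is never observed. Scores returned from home would also show whether patients without a two-year rotation measurement differ in function from those who attended. Counts of available data cannot show that.

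**Working it through.** **1. Reading the text.** Three sections, side by side:
- Data Collection: questionnaires are completed at the clinic appointment, together with the examination.
- Schedule of Events: both are marked at the same visits, with ±4 months at two years.
- Data Analysis: no imputation, and two-group tests.

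If all three are followed literally, no visit within the window means no two-year score and no place in the two-year functional comparison.

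**2. Inputs for an illustration of size.**
- From the documents: 85 enrolled, 1:1 (Randomization); 35 per group, 70 in total, effect size 0.68, 80% power, significance level 0.05 (Sample Size).
- Assumed: a two-sided test, which reproduces Table I; equal arms; no Bonferroni adjustment; the number who miss the visit; the number who return questionnaires remotely. The documents give none of the last two, and no SD for any questionnaire, so effects are in SD units.

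**3. The plan's own figure.** For effect size 0.68, the exact two-sample t-test needs 34.94 per group, so 35, with power 80.1%. The detectable rotation differences are 0.68 × 8 = 5.44° and 0.68 × 18 = 12.24°, against 5.4° and 12.2° in the plan. The figure reproduces.

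**4. Room for loss.** 85 − 70 = 15, and 15/85 = 17.6%. This is how many patients can be lost before the total falls below 70. The documents do not state it as an expected loss.

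**5. Detectable effect if those 15 miss the two-year visit.** To a close approximation, with n per group and df = 2n − 2,

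d = (t[0.975, df] + t[0.80, df]) × √(2/n).

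| Remote returns | Patients with a score | n per group | Missing scores | Detectable effect |
|---|---|---|---|---|
| 0 | 70 | 35 | 15/85 = 17.6% | 0.68 SD |
| 4 | 74 | 37 | 11/85 = 12.9% | 0.66 SD |
| 8 | 78 | 39 | 7/85 = 8.2% | 0.64 SD |
| 15 | 85 | 42.5 | 0% | 0.61 SD |

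**6. Other rates of missed visits.** If 20% miss the visit (68 attend), the detectable effect is 0.69 SD with no returns and 0.65 SD if half return. If 30% miss it (59.5 attend on average), it is 0.74 SD and 0.67 SD. Power at an effect of 0.68 SD, with no returns and with half returning:
- 17.6% missed: 80.1% and 84.0%
- 20% missed: 78.9% and 83.5%
- 30% missed: 73.2% and 81.3%

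**7. Bias.** No calculation is possible. The documents say nothing about how attendance relates to function.

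**The case against.** The strongest reply is that the plan is silent about a contingency rather than restrictive. A reader might infer that remote completion is ruled out, and the documents do not say so. What stands is that they provide no route, no rule for counting a returned form and no record of mode, so a team following the text would not collect the score.

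A second reply concerns size. A reader might take 85 against 70 as a forecast that 17.6% will be lost, and might assume that most of those scores could be recovered. Neither is supported. No dropout rate is given, and Enrollment and Consent lets patients leave at any time; those who withdraw or cannot be reached would not return a mailed form either. The gain could be nil. Nor can 0.68 versus 0.64 SD be judged clinically, because the trial is sized on rotation in degrees and no important difference is given for the questionnaires. This reply stands in full, so the figures are illustrations.

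Third, a reader might infer that a non-attender has no functional data at all, or that the comparison is shown to be biased. The patient may have baseline and earlier postoperative scores; only the two-year score is lost. Patient and examiner are blinded, which makes attendance driven by knowledge of the allocation less likely. Bias is possible, not demonstrated.

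Fourth, the plan has protections: a discussion before consent, calls before each time point, standard-of-care visits, an eight-month span at two years, and reporting of available data. These help with late attenders. They do nothing for a patient who is willing to answer but cannot come.

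**Conclusion.** The point holds as an inexpensive improvement to data collection for the secondary objective. It is not a contradiction or a calculation error in the plan. As written, a patient who does not attend within ±4 months of two years has no two-year questionnaire score and drops out of that comparison, for a reason that the instruments themselves do not impose.

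The precision effect is modest: in the 15-missed illustration, remote returns lower the detectable effect by anything from 0 to about 0.07 SD (0.679 − 0.615 = 0.064 before rounding). That range rests on assumed missed-visit and return numbers, equal arms, a two-sided 0.05 level and no Bonferroni correction. The possible bias is the better reason to act, but its direction and size are unknown. The primary rotation endpoint gains no data from the change.

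**What to change.** In Data Collection and in the questionnaire row of the Schedule of Events, state that:
- a patient still in the study who cannot attend within the window is sent the same questionnaires by mail or email, with the call already planned as the reminder;
- a form returned within the same window counts for that time point;
- the mode of completion is recorded.

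In Data Analysis, add a sensitivity analysis restricted to scores completed in clinic.

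The cost is protocol wording, postage or email, and one additional analysis. The calls are already planned, and mail or email is already offered for the consent form. The downside is that some scores would be completed at home rather than in clinic. The documents do not address whether the two are equivalent, which is why the mode should be recorded and the sensitivity analysis reported. Examination visits, sample size and the primary endpoint do not change.

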## DEMOGRAPHICS AND OPERATIVE

- Name
- Age
- Gender
- BMI
- Comorbidities, as recorded by anesthesiology
- Date of surgery
- Laterality
- Dominant hand

## PATIENT REPORTED OUTCOMES

- American Shoulder and Elbow Surgeons' Score (ASES)
- Western Ontario Osteoarthritis of the Shoulder Score (WOOS)
- Patient-Reported Outcomes Measurement Information System Global 10 (PROMIS-10)
- Visual analog scale (VAS) pain

## PHYSICAL EVALUATION

- Range-of-motion, measured with a goniometer (forward elevation, abduction, external rotation, internal rotation) (See Appendix A)
- Strength, measured with a dynamometer (in forward elevation, abduction, external rotation, internal rotation) (See Appendix A)
- External rotation lag sign test
- Drop arm test
- Lift off test
- Belly press test

## SCHEDULE OF EVENTS

Study Procedure	Preoperative	Surgery	3 months	6 months	1 year	2 years
Visit Window	8 wks to surgery	N/A	± 4 weeks	± 6 weeks	± 2 months	± 4 months
Review inclusion and exclusion criteria	X					
Informed consent review and signature	X					
Study group determination (randomization)	X*					
Intervention		X				
Patient-reported outcomes questionnaires (ASES, WOOS, PROMIS, VAS)	X*		X	X	X	X
Physical exam (range-of-motion and strength)	X*		X	X	X	X
Standard-of-care x-rays	X*		X	X	X	X

Assess for adverse events	X*	X	X	X	X	X
---------------------------	----	---	---	---	---	---

\*Consent will happen before any study procedures or assessment are done and randomization will occur at that time

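### Randomisation at consent, up to 8 weeks before surgery, lets randomised patients be lost before baseline or treatment; opening the envelope later would protect the analysed sample cheaply

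*Combined protocol and SAP*

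**What the plan says.** - **Allocation.** The Schedule of Events footnote reads "Consent will happen before any study procedures or assessment are done and randomization will occur at that time". The Randomization section matches it: "After the patient is consented, they will be assigned to a group following the treatment listed in the envelope".
- **Baseline.** Data Collection places baseline data ahead of the "procedure, after consent has been signed". It does not require baseline to be complete before the envelope is opened.
- **Window.** The preoperative visit window is "8 wks to surgery". That is an outer limit; the usual interval from consent to surgery is not given.
- **Eligibility.** Under Enrollment and Consent, "Patients that meet all criteria will be contacted by personnel on the delegation of authority as a consent provider before their procedure". The schedule row "Review inclusion and exclusion criteria" is marked in the preoperative column only.
- **Withdrawal.** Enrollment and Consent allows a patient to leave at any time, including ahead of the operation.
- **Safeguards already present.** The patient and the coordinator who examines the patient are blinded (Randomization; Data Collection). "Logs will be maintained by the randomizing personnel". On retention, "To help prevent dropouts, follow-up requirements will be discussed with the patient before consent", and patients are telephoned as each visit approaches. Data Analysis promises the number of data points at each postoperative visit and no imputation. It does not name an analysis population, promise these counts by arm, or mention patients who were randomised but not operated on.

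**The concern.** Nothing in the plan needs the allocation to be known at consent. The surgeon needs it at the operation. Every week between the two is time in which a randomised patient can withdraw or have surgery cancelled, and early allocation makes that patient a randomised patient with no outcome. If the envelope were still sealed, the same patient would simply not have been randomised, and the place could go to someone else.

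What is at stake is the number analysed at two years. The plan enrols 85 and justifies 70 without explaining the difference. If those 15 are meant to absorb losses, early allocation makes them cover losses before surgery as well as two years of follow-up. A secondary matter is accounting: as written, patients lost before surgery need not appear in the report at all.

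**Working it through.** **1. Order of events.** The footnote puts consent before any study assessment and randomisation at consent. Data Collection puts baseline after consent. Read together, allocation precedes baseline. No single sentence says so outright; it follows from the two.

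**2. The plan's own sample size.** Inputs from Sample Size: effect size 0.68, 80% power, significance level 0.05, SD 8° to 18°, important difference 14° to 22°. A two-sample t-test with two-sided alpha 0.05 needs 34.94 per group, so 35, with power 0.801. This reproduces Table I. A one-sided calculation gives 27 (normal approximation) and does not match.

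**3. The margin.** 85 − 2 × 35 = 15 patients; 15/85 = 17.6%. The plan does not say that this is a loss allowance.

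**4. Illustrative losses.** The documents give no rates. The 4 and 9 patients lost before surgery, and the two later-loss rates, are assumptions. Analysed = (85 − lost before surgery) × (1 − later loss).

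| Lost before surgery | Operated | Later loss | Analysed | Power at effect size 0.68 |
|---|---|---|---|---|
| 0 | 85 | 10% | 76.5 | 0.84 |
| 4 | 81 | 10% | 72.9 | 0.82 |
| 9 | 76 | 10% | 68.4 | 0.79 |
| 0 | 85 | 17.6% | 70.0 | 0.80 |
| 4 | 81 | 17.6% | 66.7 | 0.78 |
| 9 | 76 | 17.6% | 62.6 | 0.75 |

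Power uses half the analysed number per group, except that the last two rows are rounded down to 33 and 31 per group.

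**5. In degrees, for the 17.6% rows.** The effect size detectable with 80% power is 0.679, 0.700 and 0.723 for 35, 33 and 31 per group.
- SD 18°: 12.2°, 12.6°, 13.0°.
- SD 8°: 5.4°, 5.6°, 5.8°.
- Power for 14° at SD 18°: 0.89, 0.88, 0.85.

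At alpha 0.05, all of these stay inside the 14° lower limit of the important difference.

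**6. Effect of the Bonferroni correction.** Data Analysis plans one without giving a divisor. With an assumed divisor of 2 (alpha 0.025), the detectable difference at SD 18° is 13.5°, 13.9° and 14.4° for 35, 33 and 31 per group, and power for 14° is 0.83, 0.80 and 0.78. The reassurance in step 5 therefore depends on alpha being 0.05.

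**The case against.** Randomising at consent is an accepted design. Eight weeks is only the edge of a window, both arms receive the same operation, both versions are described as standard of care, and patients do not know their arm. Nothing suggests that losses before surgery would differ by arm. All of that stands, and it is why the point concerns precision and not bias.

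The loss figures can be called pessimistic, because the 17.6% rows charge a full postoperative loss on top of the loss before surgery. That is fair. The 10% rows show the milder case, in which losing 4 still leaves power above 0.80.

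Two stronger readings are tempting, and the documents do not support either.

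- **Baseline measured after allocation is biased.** A reader might infer this from the order of events. But Randomization keeps both patient and data collection blinded, and Data Collection uses a blinded coordinator.
- **The physical therapy exclusion removes patients after allocation and so biases the comparison.** A reader might infer this because therapy normally follows surgery. But the plan uses the word undergoing prospectively elsewhere: Research Design and Inclusion Criteria apply it to patients not yet operated on. All criteria must be met before the patient is contacted, eligibility review is preoperative only, and there is no removal rule. The natural reading is planned therapy, and nothing suggests that removals would differ by arm.

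**Conclusion.** The point holds as a matter of timing. The plan allocates at consent, ahead of study assessments and possibly 8 weeks before surgery, while allowing withdrawal in between. Randomised patients can be lost before baseline or treatment, at the expense of a 15-patient margin whose purpose is not stated.

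The size is modest. Under the assumed losses of 4 to 9 patients, power at effect size 0.68 is about 0.82 to 0.79 with 10% later loss and 0.78 to 0.75 with 17.6%, at alpha 0.05. Any Bonferroni correction lowers these, and moving randomisation would not solve that separate issue. Actual loss rates are unknown, so the true cost could be close to nil.

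No claim is made that the primary comparison is biased or undermined, or that the therapy exclusion distorts it. The change is worth making because it is inexpensive.

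**What to change.** - **Schedule of Events footnote and Randomization.** Set the order as: consent; baseline assessments; confirmation of all eligibility criteria, with the therapy criterion judged on the preoperative plan; then the envelope opened as close to surgery as practicable, by the same personnel who now do it.
- **Data Analysis, one supporting sentence.** State that operated patients are analysed in their allocated group, and that patients randomised but not operated on are reported by arm. The existing randomisation logs can supply the counts.

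The timing change reduces only the losses before surgery. It does not affect losses during follow-up, and the surgeon must still be told the group. The cost is protocol wording, with no added visits or patients. The one practical burden is that randomising personnel must be reachable near the time of surgery.
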